Results of this study may be used for presentations, posters or publications. The publications will not contain any identifiable information that could be linked to a subject and will be reviewed by the Sponsor prior to publication.

Sharing of Results with Subjects

Results will not be shared with subjects.

Data Analysis and Evaluation Techniques

This study will help to develop protocol and standards for in diagnostic CTC test in vivo for using in routine clinical practice for melanoma patients. The obtained results will be published in the peer-reviewed journals, presented at the conferences and used in gaining broader approval of the technology by regulatory agencies. The data analysis will be conducted as outlined below.

Analysis plan for Group1 (healthy subjects): The study will provide data for the optimization of technical parameters of PA probes that do not require special statistical consideration. Specifically, it will include medium types for acoustic coupling of transducer and skin, method of visualization of laser beam on the skin and vessels, mechanical holder for spatial fixation of PA probe near skin, and signals from blood vessels.

We will define beforehand a window of equivalence with upper and lower limits of equivalence. For example, if we want the two signal amplitudes to be similar to within $\pm 30\%$, then the window of equivalence would have an "upper limit of equivalence" at +30% and a "lower limit of equivalence" at -30%. Measure 20 blood vessels in the dorsal side of the hands of 3-5 individuals. We can use both hands from the same person. On each vessel, we will use both lasers in second mode for vessels only (background signals). Then we will calculate the difference in signal amplitudes from each laser. We will express the difference as a percentage relative to skin background without visible vessel as well as the percentage relative to Laser 1, or the percentage relative to 0.5*(Laser 1 + Laser 2). Then we will calculate the mean of the percent differences and calculate the 90% confidence interval on that mean. If both ends of the 90% confidence interval fall inside the window of equivalence (i.e., if both ends fall in between the upper and lower limits of equivalence), then you will have established that the two lasers give background signals from vessels only whose signal amplitudes are equivalent to within $\pm 30\%$.

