After signing the IRB-approved informed consent form, research subjects will be registered on the clinical site performing the Cytophone test. At that time, a registration number will be provided to the Principal Investigator and research staff. The initial procedure must be conducted within 90 days of consent, or the subject will be withdrawn from the study and will need to re-consent in order to participate. Subjects who are withdrawn from the study due to delay of procedure may be replaced.

All these forms clearly indicate the participation in the study is voluntary.

Consent Methods

The informed consent form will be presented to participants at the first visit. The consent process will occur in a private room with the research nurse. A research member will explain the informed consent form for each potential participant. All participants will be given the option to ask questions, they will be given ample time to consider participation and the benefits and risks associated with that participation. The participants will be asked to sign the informed consent upon agreement of the terms and conditions associated with the study. Participants will also indicate that they have read the consent form and agree to participate by selecting 'yes' on the consent form page.

Participants can withdraw from the study at any time without any consequences.

Signed consent documents returned via fax, email, or mail should be accompanied by copies of official documentation identifying the potential subject and witness. Consent documents returned by any of these methods will be signed/dated by study staff with the current date. The consent process will be documented in the medical record. The original informed consent will be filed with the subject file. Each participant will be given a copy of the informed consent.

Potential Risk/Benefits to Subjects or Others

Risks.

Minimal risks are expected because the Cytophone (PAFC) device with the same lasers and the same parameters was approved by the IRB committee at the University of Arkansas for Medical Science (Protocol #133965) and the FDA classified this device as a Non-Significant Risk (NSR) medical device with the Investigational Device Exemption (IDE). Moreover, clinical testing of melanoma patients in vivo using PAFC with the same parameters revealed no adverse effects.⁷ Thus, The Cytophone is regarded as safe but may cause:

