- Local skin irritation and redness as well as burning, tingling, itching, stinging or localized pain sensations; careful monitoring of skin changes will be provided and local treatment including ice pack, skin lotion or topical steroid will be provided as needed.
- Discomfort during sitting for the time required to complete the procedure; the participant may request that the procedure be stopped at any time.

Risks associated with blood draws may include bruising, minor pain and rare infection at the puncture site. Experienced personnel will perform this procedure using approved techniques. Pressure and dressings will be used to minimize pain, bruising and infection.

There is also a minimal risk associated with loss of confidentiality or anonymity. To minimize this risk, participants' identity will be kept confidential at all times by the research team. Subjects will be assigned a study number unrelated to their medical record number or other personally identifying information. The obtained research data will be associated with the subject's number only. The key to the participant identity will be kept in a locked file cabinet behind a locked door that only the research team will have access to. Signed consent forms will also be kept in this locked file cabinet but separate from the data.

No risks to others are anticipated.

Benefits.

While there are no direct benefits to the participants in this study, results may help practitioners to better understand the Cytophone (PAFC) diagnosis and use it in future as an advanced test for early melanoma diagnosis, early detection of disease recurrence, monitoring of therapy efficiency, and potentially melanoma screening.

Safety Endpoints

If any of the participants reveal procedure-related side effects or Adverse Events (AEs), the subject will be withdrawn. If three people are withdrawn for that reason, the study will be stopped.

Withdrawal of Subjects

Subjects will be withdrawn from the study if:

- 1. The Investigator considers it would be in the best interest of the subject (e.g., AEs, intercurrent illness or onset of new clinically significant condition).
- 2. Female subject becomes pregnant.
- 3. There is a protocol violation which increases the risk to the subject.
- 4. Subject withdraws consent or is lost to follow-up.

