The subject will be contacted immediately to schedule a withdrawal visit. If the subject cannot be reached on first attempt, then a second and third attempts to contact the subject via phone and email will be made.

If and when a subject withdraws from the study for any reason, all efforts will be made to complete and follow the participant through observations as thoroughly as possible. A final evaluation will be attempted in those willing to participate.

Provisions to Monitor the Data to Ensure the Safety of Subjects

AEs and safety labs will be reviewed at each visit by the PI. Additionally, subjects will be instructed to call the study team to report new symptoms/AEs. These AEs will be recorded in the subject's binder on a cumulative AE log. If a serious AE is unresolved when a subject permanently discontinues the study, the subject will be followed until the AE resolves, or the clinical course is stabilized.

An independent safety monitoring committee involving a physician ([name]), engineer ([name]) and bio-statistician (TBD) will review safety labs and AEs after the first 5 subjects are enrolled and then after the 50th and 100th subjects are enrolled. He/she will notify the study team if he determines that the study must stop for safety concerns and will be charged with the responsibility of determining if the trial needs to be stopped based on lab criteria and data from any unexpected AEs. These unexpected AEs will be promptly reported to the independent safety monitoring physician.

The whole study will be stopped in cases where serious AEs are experienced by 3 or more subjects and are not deemed unrelated to participation in the study by the PI or the independent safety monitoring committee. Any AE will be immediately communicated to the PI in writing notifying of the event(s).

Provisions to Protect the Privacy Interests of Subjects

All subject interactions will occur in a private room or lab setting. Subjects will be introduced to the various study team members by the PI or study coordinator with whom they've already established a relationship through prescreening or the consent process.

The research team will obtain consent prior to receiving any information about subjects.

Subject Compensation/Reimbursement

There could be compensation for participating in this study. The compensation would be paid on a per visit basis, and only paid once each visit is completed for the study.

Data Management and Confidentiality

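### Three minor procedure-related skin reactions would, read literally, stop the study; the Safety Endpoints rule has no severity limit and is not reconciled with the Risks, withdrawal and serious-AE stopping text

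*Protocol*

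**What the plan says.** Four places in the protocol bear on this.

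- **Safety Endpoints.** "If any of the participants reveal procedure-related side effects or Adverse Events (AEs), the subject will be withdrawn". The next sentence reads "If three people are withdrawn for that reason, the study will be stopped". Neither sentence carries a condition on severity, seriousness or expectedness.
- **Potential Risk/Benefits to Subjects or Others, Risks.** "The Cytophone is regarded as safe but may cause" introduces a short list whose first item is "Local skin irritation and redness as well as burning, tingling, itching, stinging or localized pain sensations". Skin changes are to be monitored, and "local treatment including ice pack, skin lotion or topical steroid will be provided as needed". Withdrawal is not mentioned there. The same section says that minimal risks are expected and that earlier testing of melanoma patients with the same device parameters showed no adverse effects.
- **Withdrawal of Subjects, item 1.** AEs appear as an example under a judgement: "The Investigator considers it would be in the best interest of the subject".
- **Provisions to Monitor the Data to Ensure the Safety of Subjects.** "The whole study will be stopped in cases where serious AEs are experienced by 3 or more subjects", provided that these events "are not deemed unrelated to participation in the study by the PI or the independent safety monitoring committee". The PI reviews AEs at each visit and is told of any AE in writing. The safety committee reviews after the first 5, the 50th and the 100th subject enrolled.

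No section refers to another on this subject.

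**The concern.** Redness or tingling under the probe is, on its face, a procedure-related side effect. The Risks text treats it as something to watch and soothe. Safety Endpoints treats the same event as compulsory withdrawal and as one third of the way to closing the study. A site reading one section would keep the subject; a site reading the other would withdraw the subject and add to the count.

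At stake are the objectives that need time. Groups 2-4 are to have PAFC at Day 0 and Months 3, 6 and 9, followed by observation of medical records, OS and PFS. The primary objectives, linking a positive test to metastasis risk and finding count thresholds, depend on that series and on those outcomes. A stop after three trivial reactions could come before either is complete. Short of a stop, each affected Group 2-4 subject with visits remaining would leave serial testing.

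**Working it through.** The protocol states no event rate and no operating characteristic for either stopping rule, so there is no figure to reproduce. The check is mainly textual.

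**Sections side by side**

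| Point | Safety Endpoints | Elsewhere |
|---|---|---|
| Minor local skin effect | Withdraw; counts toward the stop | Risks: monitor and treat locally; withdrawal not mentioned |
| Withdrawal for an AE | Mandatory | Withdrawal list: investigator's judgement |
| Study stop | Three withdrawals, any severity | Safety monitoring: serious AEs in 3 or more subjects, not deemed unrelated to participation |
| Who decides | Not named | Safety monitoring: PI or committee judges relatedness |

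**The trigger phrase.** *Procedure-related* may qualify both *side effects* and *Adverse Events*, or only the former. On the second reading an AE from any cause withdraws the subject. What follows uses the narrower reading, under which only procedure-related events count.

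**How the two stops overlap.** The serious-AE stop acts alone for serious events of uncertain cause, and for those related to participation but not to the procedure. For clearly procedure-related events the Safety Endpoints stop will usually be reached first, because it has no seriousness condition. That order is not guaranteed. One rule counts withdrawals and the other counts subjects with events, and a subject past the last procedure may have nothing left to be withdrawn from.

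**Size of the trigger.** Planned enrolment is 180 (30 healthy, 150 with melanoma; Subject Population section). 3/180 = 0.0167, or 1.7%.

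**Illustration with assumed rates.** Let p be an assumed chance that a subject has any procedure-related effect, with subjects independent. Then

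P(at least 3 of n) = 1 − Σ(k = 0 to 2) C(n,k) p^k (1−p)^(n−k).

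For n = 180 and p = 0.01 the three terms are 0.164, 0.298 and 0.269, so the result is 1 − 0.731 = 0.269.

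| Assumed p | n = 180 | n = 100 |
|---|---|---|
| 0.5% | 0.062 | 0.014 |
| 1% | 0.269 | 0.079 |
| 2% | 0.700 | 0.323 |

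The n = 180 column is the chance of three affected subjects at any time in the study, so it does not measure early stopping. The n = 100 column takes p as the rate at the first procedure. It gives the chance that the third affected subject is among the first 100 enrolled, with 180 − 100 = 80 still to come. Every p is an assumption; the table shows sensitivity and is not a forecast.

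**The case against.** The strongest reply is that nothing here is contradictory. A subject can be given an ice pack and also withdrawn. A Risks section need not mention withdrawal, which has its own section. The withdrawal list is not exhaustive (a delay beyond 90 days from consent is another ground, given under Recruitment Methods), so a specific mandatory rule can stand beside a general discretionary one. The two stops can both be applied. A sponsor who anticipates almost no events, in a study without direct benefit to participants, may want a very cautious stop. The PI already receives the information needed for the count.

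Most of this stands, and it rules out several stronger readings that a reader might infer:

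- *That the Risks text expects these effects.* It says that the device may cause them, and it reports none in earlier testing of melanoma patients.
- *That the two stopping rules conflict, or that one makes the other redundant.* They can be obeyed together, and each can act alone.
- *That every affected subject loses serial data.* The Study Calendar gives Group 1 a single PAFC test, and a subject first affected at visit 4 has no measurement left to lose. The Withdrawal section also calls for efforts to keep following withdrawn subjects.

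The reply does not show that a stop after three cases of transient redness is intended. Nor does the report of no adverse effects settle the matter. If it covers the 28 patients described in the Study Summary (an assumption), zero events in 28 gives a one-sided 95% upper bound of 1 − 0.05^(1/28) = 10.1% per subject, well above the rates in the illustration.

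**Conclusion.** The point holds as a failure to reconcile sections. As written, three procedure-related effects of any severity, 1.7% of planned enrolment, close the study, although the Risks text handles such effects by local care. This is more than missing detail, because following the Safety Endpoints rule to the letter could defeat the study's serial and follow-up objectives.

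The conclusion rests on the literal wording and on the narrower reading of the trigger. It does not rest on the probabilities. A reader might infer from them that an early stop is likely. The protocol does not support that: it gives no rate, and the illustrative results run from 1.4% to 70% according to what is assumed. Nor do they argue for another threshold.

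**What to change.** Reconcile the Risks text, Safety Endpoints, Withdrawal of Subjects and the safety monitoring section, so that the protocol states:

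1. whether minor local effects of the kind listed under Risks trigger withdrawal and count toward the stop;
2. whether withdrawal for a procedure-related effect is automatic or at the investigator's judgement;
3. whether *procedure-related* qualifies *Adverse Events* as well as *side effects*;
4. how the two stopping rules relate, and who applies the Safety Endpoints count.

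Which rule and which threshold to adopt is for the sponsor and the safety committee. The cost is a protocol amendment to the wording, with no extra patients or procedures.

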To achieve our goal, we will accomplish the following **primary and secondary objectives**:

The primary objectives:

- 1. Obtain evidence that positive PAFC-based CTC test indicate a risk of metastasis development
- 2. Define thresholds of CTC counts that correlate with melanoma recurrence and progression of metastatic disease and therapy efficacy

The secondary objective:

1. Determine if PAFC diagnoses risk of melanoma metastasis progression and recurrence earlier than existing methods.

Background

Worldwide, more than 350,000 people are diagnosed with melanoma and nearly 60,000 deaths are attributed to melanoma annually.⁸ In the US, melanoma is the fifth most common cancer (https://www.cancer.net/cancer-types/melanoma/statistics) resulting in a high mortality rate. According to the American Cancer Society (https://www.cancer.org/cancer/melanoma-skin-cancer/about/key-statistics.html), the estimates for melanoma in the US for 2023 is about 97,610 new cases, and about 7,990 people are expected to die of melanoma. The main cause of melanoma deaths is metastasis.^{1,8-9} Indeed, the localized primary tumors can be effectively treated, but if tumor cells detach from primary tumor, prognosis worsens, and treatment becomes much less effective. As an example, the 5-year relative survival rate in patients with "thin melanoma," with no detectable metastasis is 99% while it dropped to 32% for patients with metastatic melanoma.⁹

Despite remarkable progress which has been made on both the diagnosis and therapy of metastatic melanoma, the incidence, recurrence, and death rates remain unacceptably high.⁹

It is important that (1) a median delay of early melanoma diagnosis is estimated at approximately 9 months;^{8,10} and (2) many people still don't benefit from the newest drugs because of melanoma recurrence after initial successful treatment.¹¹ Thus, new diagnostic tools to identify early melanoma, especially, its risk to metastasis progression and risk of recurrence in melanoma patients are of paramount importance for surveillance and treatment plans.

Based on our comprehensive literature review, diagnostic challenges that need resolved are outlined below.

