- 3. Group 3: The Cytophone testing of 50 subjects who have been pathologically diagnosed with Stage II melanoma. The initial PAFC testing will occur within 30 days of diagnosis. Subjects will have 4 visits. The first visit will include checking eligibility + signing a consent form, blood draw and the Cytophone's testing. The follow-up three visits (visits 2, 3 and 4) will include the Cytophone's testing. An increase in CTC count will possibly demonstrate an early sign of initiation of disease progression. Group 3 participants will be asked to provide their ID number in order to link their in vivo CTC count with medical records including dermoscopy, biopsy, sentinel lymph node (SLN) status, CT, MRI, PET and others. The results will be used to analyze the correlation between CTC count and metastatic disease initiation/progression and further recurrence induced by metastasis-originated CTCs.
- 4. Group 4: The Cytophone testing of 50 subjects who have advanced-stage melanoma (stages III IV) with metastatic disease. Subjects will have 4 visits. The first visit will include checking eligibility + signing a consent form, blood draw and the Cytophone's testing. The follow-up three visits (visits 2, 3 and 4) will include the Cytophone's testing. Dynamic of CTC counts will be defined over disease progression and treatment to link CTC counts, metastatic disease progression and therapy efficiency. Group 4 participants will be asked to provide their ID number in order to link their in vivo CTC count with medical records.

Visits. The study will last less than two years and will includes 4 visits, and 12 months follow-up observation of medical records, OS and PFS after 4th visit.

Visit 1 (90 minutes) – at any time in Group 1, after the diagnosis of melanoma in Groups 2-4. The visit will start with checking inclusion and exclusion criteria, confirming eligibility, and obtaining the informed consent. **Only subjects who are eligible and have signed off on the consent form will participate in this study**. Next, the visit will involve blood collection, ultrasound imaging, adjustment PAFC laser beam on the vessel and PAFC monitoring. Also, information on possible adverse events and review of medications and diagnostic tests will be collected, and vital signs (temperature, pulse, blood pressure) will be measured. A pregnancy test will be done if the subject is a female of childbearing potential.

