Pregnancy testing: serum pregnancy tests will be carried out for women of child-bearing potential.

Collected data.

Demographic data, diagnosis, medical records, and medications will be collected at the first visit (pre-visit). Medical records, and medications will be continuing to monitor over a period of 4 clinic visits (~ 9 months) and a post-12-month observation.

The Cytophone records will be use to:

- Collect background signals in vivo and in vitro to estimate rate of false positive signals (Croup 1)
- Calculate number of PA signals per a time unit that are associated with single CTCs and CTC clusters (Groups 2-4)

At the end of the monitoring and observation period, the investigators will analyze the results and determine if the CTC counts correlate with metastatic disease progression and may be used as diagnostic and/or prognostic criterium of aggressiveness of early melanoma, initiation/progression of metastasis, initiation/progression of recurrence and assessment of therapy efficacy.

Photographing Participants.

Participants will be asked a yes or no question on the informed consent as to whether they agree or not to allow the research staff to take an ultrasound images and photo during testing for presentation purposes ONLY. They will be no identifying facial pictures taken.

Study Calendar

	Visit 1; Day 0	Visit 2; Month 3 (± 14 Days)	Visit 3; Month 6 (± 14 Days)	Visit 4; Month 9 (± 14 Days)	Observation of medical records, OS and PFS; Month 24 (± 14 Days)
Group 1					
Informed consent	Х				
Inclusion/Exclusion criteria	Х				
Vital signs/pregnancy test	Х				
PAFC	X				
Photography	X				
Blood sampling					
Review AEs / Medications / Medical records	X				
Group 2-4					
Informed consent	X				
Inclusion/Exclusion criteria	X				
Vital signs/pregnancy test	X	Х	X	Х	
PAFC	X	Х	X	X	
Photography	X	X	X		
Blood sampling	Х				

Review AEs /	Х	Х	Х	Х	Х
Medications /					
Medical records					

Description of New Device and monitoring procedure

The Cytophone device is based on a noninvasive, label-free PAFC diagnostic platform (**Fig. 2**). The Cytophone will be used to monitor in vivo (1) healthy volunteers to optimize The Cytophone's parameters and estimate false signal rates, and (2) melanoma patients to identify the presence of melanoma CTCs and their clusters (aggregates, clots), and to enumerate them per a time unit.

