Subjects will receive PAFC procedure while seated in a chair. The subject's hand will be placed on a customized surface, with a PAFC probe placed over a selected vein. Acoustic contact between the skin and ultrasound transducer will be provided by a gel. Flexible Velcro strips is used to provide gentle fixation of the hand during PAFC monitoring. PAFC will be used to monitor blood flow during 30 min. If necessary (e.g., due to signal instability or low signal levels) this procedure will be repeated on a different blood vessel(s) up to an additional 30 minutes. PA measurements will be performed the entire time the subject holds the hand under the probe. The position of the probe over the vein will be monitored, if necessary, by comparing the signals from blood vessel to that from surrounding tissues and may require adjustment during the experiment.

While the device is contained on a cart, it remains in one location, except when maintenance requires moving it to the company. If the device is moved for maintenance, it is recalibrated after returning it to the clinical site.

Subject Population and Inclusion/Exclusion Criteria

Study Population: To achieve our goal, we expect to enroll 180 participants (18-80 years old) during the proposed timeframe. Males and females will be eligible for this study. No exclusions will be made regarding ethnicity. The target is to enroll 20-25% of subjects with dark skin.

Prior to coming in for the Cytophone's testing, subjects will sign the consent and complete a medical history questionnaire.

Group 1: 30 healthy subjects, twenty of whom will be of light skin tones and ten of which will be of dark skin tones according to the Fitzpatrick classification scale.

Groups 2-4: 150 subjects (50 subjects per a group) with melanoma will be assigned to study based

on the AJCC Melanoma of the Skin Disease Staging (8th edition) as documented at the time of consent based on current or previous disease status.

All participants will receive 4 PAFC procedures over ~9 months. A blood sample will be taken for in vitro CTC and ctDNA tests.

Inclusion and Exclusion Criteria

Inclusion Criteria for Group 1 (Healthy Subjects):

- Aged 18–80 years, inclusive
- Free of concomitant or previous malignancies, as deemed by the Principal Investigator, is not contraindicated with any past medical history of the participant

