CTC counts per a time unit in vivo and in vitro as well as ctDNA concentration at Day 0, Month 3 or after surgery, Month 6, Month 9 and Month 12 will be calculated and averaged with coefficients of variation. The increasing trend of CTC counts will be estimated and correlated with other signs of metastasis initiation/progression.

All subjects entered into the study at the first visit will be included in the safety analysis. The frequencies of AEs by type, body system and severity will be summarized. Severe AEs will be described in detail.

Identifiers collected will be entered directly into a prescreening form, which is password protected. If the potential subject fails prescreening, identifiers will not be collected. If the potential subject declines to participate, identifiers will be destroyed upon declination. If the potential subject signs consent, their name and email address will be copied to a screening log in and removed from the prescreening form. Any remaining information on the prescreening form will be permanently deleted from the system when prescreening closes. PHI will not be reused/disclosed to any other

person or entity except as required by law, for authorized oversight of the research, or for other research which use/disclosure of PHI would be permitted by the HIPAA privacy regulations. Identifiable information collected during prescreening (names, email addresses) will only be collected if the potential subject meets the eligibility criteria. Health information will not be recorded during prescreening but will be reviewed to confirm eligibility.

Conflict of Interest

[name] has a proprietary interest in the device, which is associated with CytoAstra, LLC as she is an inventor of PAFC (Cytophone), that have obtained US Patents, 11154360 and 11259705. She is also employed by CytoAstra. To prevent any COI concerns, [name] will NOT have direct contact with human subjects on this study at any time or will not try to recruit subjects for this study.

Drs. [name], [name], and [name] have a proprietary interest in the device associated with CytoAstra, LLC. They are currently employed by CytoAstra. They will serve as operators of the device and will only be referred a subject ID when administering the device. Communication will only be limited with the subject to successfully administer the device.

Dissemination of Data

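### The stated correlation of CTC trend with progression does not require the counts to come first, so a rise that follows progression could be reported as prognostic

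*Protocol*

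**What the plan says.** **Objectives (Study Summary).** Primary objective 1 is to "Obtain evidence that positive PAFC-based CTC test indicate a risk of metastasis development". The secondary objective is to "Determine if PAFC diagnoses risk of melanoma metastasis progression and recurrence earlier than existing methods". Both are claims about order in time.

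**Marker window.** For the melanoma groups, Study Population states "All participants will receive 4 PAFC procedures over ~9 months", and the Study Calendar places them at Day 0 and Months 3, 6 and 9. The summary paragraph in Data Management and Confidentiality also lists a Month 12 value ("Month 6, Month 9 and Month 12 will be calculated and averaged with coefficients of variation"), but no visit supplies one.

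**Outcome window.** Collected data says records and medications will be "continuing to monitor over a period of 4 clinic visits (~ 9 months) and a post-12-month observation". The Visits section gives "12 months follow-up observation of medical records, OS and PFS after 4th visit", which is Month 9 + 12 = Month 21, while the Study Calendar prints Month 24.

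**Analysis.** Data Management and Confidentiality says "The increasing trend of CTC counts will be estimated and correlated with other signs of metastasis initiation/progression". Collected data says that at the end of observation the investigators will "determine if the CTC counts correlate with metastatic disease progression and may be used as diagnostic and/or prognostic criterium". The analysis plan for Groups 2-4 covers in vivo versus in vitro detection, agreement between methods and laser equivalence. It does not relate counts to outcome.

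**The concern.** The marker window lies inside the outcome window. A subject who progresses at Month 2 or Month 5 still contributes later counts, taken after the event, to the trend that is then correlated with that event. A correlation of this kind cannot tell CTCs that rise before progression from CTCs that rise because of it.

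The Protocol intends to draw prognostic conclusions from this. Collected data names a prognostic criterion as a possible use, and the Group 3 description offers a rise as a possible early sign of progression. A marker that only lags progression could then be presented as evidence for primary objective 1 and for earlier diagnosis. A SAP that carried the sentence over unchanged would inherit the problem.

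**Working it through.** The Protocol gives no power, event rate or variance for this correlation, so there is no figure to reproduce. The check asks how often a marker with no predictive value would be called favourable.

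**Inputs from the Protocol.** Visits at t = 0, 3, 6 and 9 months; 50 subjects per melanoma group; outcome read at Month 24 (calendar) or Month 21 (text).

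**Assumed inputs.** Progression by Month 24, p = 5–50%, with constant hazard; rise after progression of 2- or 3-fold, so δ = log10(2) = 0.30 or log10(3) = 0.48; between-subject SD 0.5 log10; within-subject SD σ = 0.3 or 0.5 log10; rise lasting, or limited to 3 or 6 months.

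**Step 1: events inside the marker window.** The expected number by Month 9 is 50 × [1 − (1 − p)^(9/24)].
- p = 5%: 50 × (1 − 0.95^0.375) = about 1
- p = 20%: 50 × (1 − 0.80^0.375) = about 4
- p = 50%: 50 × (1 − 0.50^0.375) = about 11

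**Step 2: what one event does to the slope.** The slope is Σ(t − 4.5)y / Σ(t − 4.5)², with denominator 20.25 + 2.25 + 2.25 + 20.25 = 45.
- Lasting rise: progression between Visits 1 and 2 shifts the slope by δ(−1.5 + 1.5 + 4.5)/45 = 0.10δ; between Visits 2 and 3, δ(1.5 + 4.5)/45 = 0.13δ; between Visits 3 and 4, δ(4.5)/45 = 0.10δ. The average is 0.11δ.
- Rise seen at one visit only (about 3 months): −0.033δ, +0.033δ and +0.10δ, averaging 0.033δ.

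The average shift is upward in both cases, but 0.11/0.033, about 3 times, larger when the rise lasts. The SD of a slope is σ/√45, which is 0.045 for σ = 0.3 and 0.075 for σ = 0.5.

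**Step 3: simulation.** Counts carry no information before progression. Subjects progressed and not progressed by the end of observation are compared by a t-test of slopes at two-sided 5%, counting only results in the favourable direction (nominal 2.5%). With 2,000 replicates the simulation standard error is about 1 percentage point at a rate of 20%, since √(0.2 × 0.8/2000) = 0.009.

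| Setting, N = 50, 2- to 3-fold rise | False favourable calls |
|---|---|
| Lasting rise, σ = 0.3, Month 24, p = 20–50% | about 14–39% |
| Same, rise lasts 6 months | about 8–20% |
| Same, rise lasts 3 months | about 4–7% |
| Lasting rise, σ = 0.5, Month 21, p = 20–50% | about 7–21% |
| Lasting rise, σ = 0.3, p = 5% | about 6–10% |
| Short-lived rise, p = 5% | from about 3% |
| Month 9 landmark (progression-free at Month 9, later progression only) | 2–3% |

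**Step 4: events left for a landmark.** The expected number from Month 9 to Month 24 is 50 × [(1 − p)^(9/24) − (1 − p)]. This is about 6 at p = 20% and about 1.5 at p = 5%.

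**The case against.** **The sentence can be read as concurrent association.** It sits among descriptive summaries and speaks of other signs of metastasis. Read that way, it properly serves the Group 4 aim of following counts through progression and treatment, and the therapy-efficacy part of primary objective 2. This stands: counts after progression belong in those analyses, and the concurrent correlation should stay for them. It does not help the two objectives that need time order, for which no other analysis is stated.

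**Timing of covariates is usual SAP content.** That is true of detail such as a landmark or a Cox specification. Here, however, the Protocol names a method, and that method does not fit its own objectives.

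**Objective 1 concerns a positive test, not a slope.** In Groups 2 and 3 the first test falls within 30 days of diagnosis, so baseline positivity largely precedes progression. This also stands, and it limits the concern to repeated counts and trends.

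**The design can support time order.** PFS, OS and 12 months of follow-up after Visit 4 are planned. They make the fix cheap, but no stated analysis uses them to order counts and events.

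**The size is assumed.** This stands too. Group 2 (Stage 0-I) may progress rarely, and treatment may lower counts after progression. Both reduce the bias.

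**Conclusion.** The point holds. As stated, the method cannot separate a leading marker from a lagging one, so it cannot support primary objective 1 (where repeated counts are used) or the secondary objective. If counts rise after progression, the bias favours the device on average.

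Its size is uncertain. With 50 subjects it runs from about 3% false favourable calls (short-lived rise, few events) to about 39% (lasting 3-fold rise, within-subject SD 0.3, 50% progressed), against a nominal 2.5%. Progression rate, SDs, and the height and duration of the rise are all assumptions.

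A reader might infer three stronger things that the Protocol does not support:
- That a lagging rise would certainly be read as prediction. The wording is tentative, so could is as far as it goes.
- That the error is larger still because all 150 patients are pooled. No pooled correlation is stated.
- That many Group 4 subjects would die before completing a trend, using the 32% five-year survival in Background. That is a relative survival rate for metastatic disease, and applying it to a mixed stage III-IV group would need a constant-hazard assumption. The conclusion does not rest on it.

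**What to change.** Replace the sentence in Data Management and Confidentiality, and align Collected data with it:

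1. **Prognostic and earlier-detection objectives.** Use only counts taken before the first documented recurrence or progression. One suitable main analysis is a Cox model for PFS with log CTC count as a time-updated covariate (last value before each event time), stratified by stage group.
2. **Any slope analysis.** Restrict it to subjects progression-free at Month 9 and to progression after Month 9.
3. **Monitoring and therapy efficacy (Group 4, primary objective 2).** Keep the concurrent correlation, including counts after progression, as a separate descriptive analysis that is not offered as evidence of prediction.

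**Cost.** This changes analysis wording only and needs no new visits. Counts, medical records and PFS are already collected, although the date of first documented progression must be recorded explicitly. The landmark drops early progressors and may leave few events (about 6 of 50 at 20% progression and 1.5 at 5%, so Group 2 especially), which is why the time-updated model should be the main analysis. After Month 9 that model relies on the last available count.
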